45 zeros were observed. Given this heterogeneity assumption, a Bayesian hierarchical  
46 random-effects model was used to analyze the data. The assumption of our model  
47 was that the number of individuals  $y_j$  responding to influenza vaccination is  
48 binomially distributed as:

49  $y_j \sim \text{Binomial}(p_j, n_j)$ ,

50 where the success rate ( $p_j$ ) was the probability of influenza onset in mothers and  $n_j$   
51 was the number of individuals in the  $j$ th group. We note that there are only 2 groups  
52 ( $j=1,2$ ): the vaccinated and the not vaccinated groups. The probability ( $p_j$ ) itself  
53 follows a beta distribution with parameters ( $a_j, b_j$ ). Non-informative distributions  
54 priors distributions were placed on the parameters of the beta distributions. P-values  
55 of 0.05 or less were considered statistically significant. IVE against influenza was  
56 estimated as follows:  $[1 - (\text{incidence rate of influenza in vaccinated women} / \text{incidence rate of influenza in unvaccinated women})] \times 100$  [11]. The statistical analysis was  
57 conducted using R 3.6 (R Foundation for Statistical Computing).  
58

59

60

61 **Results**

62 A total of 949 pregnant women were enrolled in the study (Figure 1). Of them, 94  
63 women were excluded from the analysis because of the following reasons: lost to  
64 follow-up or decision to withdraw from the study (65 women), post-partum influenza  
65 vaccination (cocooning) (25 women), spontaneous abortion (3 women), and perinatal  
66 death (1 woman). Therefore, 855 pregnant women were included in the analysis.  
67 Their mean age was 32.9 years (range: 18-45 years) and their mean gestational age at  
68 enrollment was 23.3 weeks (range: 3-39 weeks).

69 Of the 855 pregnant women, 525 (61.4%) were vaccinated against influenza and 330  
70 (38.6%) refused vaccination. No serious adverse event occurred. Pregnant women  
71 with a history of influenza vaccination the past (2018-2019) season were more likely  
72 to get vaccinated against influenza in 2019-2020 compared to women with no history  
73 of vaccination (91.8% versus 55.1%, p-value<0.001). In the logistic regression  
74 analysis the following variables were significantly associated with a history of  
75 influenza vaccination in 2019-2020: lower gestational age (OR: 0.998; CI: 0.998-  
76 0.999), influenza vaccination the past season (OR: 8.8; CI: 4.7-16.2), and no smoking  

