77 during pregnancy (OR: 0.6; CI: 0.4-0.9).

78 ***Estimation of IVE in pregnant women***

79 Of the 855 pregnant women included in the analysis, 636 women were still pregnant  
80 during the 2019-2020 influenza season and comprised the study group for the  
81 estimation of IVE in pregnancy. Of them, 406 women (63.8%) were vaccinated  
82 against influenza and 230 (36.2%) refused vaccination. Table 1 shows their  
83 characteristics by influenza vaccination status.

84 Twelve of the 636 pregnant women tested positive for influenza (8 cases of influenza  
85 A/H3N2, 2 cases of A/H1N1 and 2 cases of influenza B). Table 2 summarizes their  
86 morbidity by influenza vaccination status. The incidence of influenza differed  
87 between vaccinated women (6/406; 1.47%) and unvaccinated women (6/230; 2.6%),  
88 however the difference was not statistically significant. Similarly, higher rates of  
89 febrile episode, ILI, pneumonia, healthcare seeking, hospitalization, use of antibiotics  
90 and antivirals were noted in the unvaccinated group compared to the vaccinated  
91 group, however none of these differences reached statistical significance (Table 2).  
92 The IVE of QIV against influenza was 43.5% for pregnant women during 2019-2020  
93 in Greece. The IVE of QIV against influenza was 43.5% (95% CI: 28.4%-55.6%) for  
94 pregnant women during 2019-2020 in Greece.

95 According to the regression model the age was not a predictor of influenza onset in  
96 the sample of pregnant women. Influenza vaccination of pregnant women reduced  
97 their logit to develop influenza by -4.2 (95% CI -3,7 -4,7), which indicates that  
98 influenza vaccination added a statistically significant protection to pregnant women.

99 ***Estimation of IVE in infants***

100 A total of 474 infants were born before or during the 2019-2020 influenza season and  
101 constituted the group for the estimation of IVE in infants. Their mean birth weight  
102 was 3189 g (range: 630-4650 g) and their mean gestational age was 39.1 weeks  
103 (range: 28-42 weeks). There were 281 (59.3%) infants whose mothers were  
104 vaccinated during pregnancy and 193 (40.7%) infants of unvaccinated mothers. The  
105 unvaccinated mothers had a mean gestational age of 31.2 weeks at enrollment  
106 compared to a mean gestational age of 28.3 weeks of vaccinated mothers (p-value

107 <0.001); no other significant difference was noted between the two groups (data not  
108 shown).

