109 Overall, 8 of the 474 infants tested positive for influenza (5 cases of influenza  
110 A/H3N2, 2 cases of influenza A/H1N1 and 1 of influenza B). Table 3 summarizes  
111 their morbidity by maternal influenza vaccination status. Infants of unvaccinated  
112 mothers more often developed influenza, febrile episodes, ILI, ARI, AOM and  
113 pneumonia and had increased rates of healthcare seeking, hospitalization, use of  
114 antibiotics and use of antiviral agents compared to infants whose mothers were  
115 vaccinated, however these differences reached statistical significance only for ARI  
116 and use of antiviral agents (p-values=0.012 and 0.036, respectively). The IVE against  
117 influenza for infants was estimated at 31.4% in 2019-2020. The IVE against influenza  
118 for infants was estimated at 31.4% (95% CI: 4%-51%) in 2019-2020.

119 According to the regression model the age of pregnant women was not a predictor of  
120 influenza onset in the sample of young infants. Additionally the influenza vaccination  
121 of pregnant women reduced the logit of their infants to develop influenza by -4.2  
122 (95% CI -3.6, -4.9), which indicates that influenza vaccination during pregnancy  
123 added a statistically significant protection to young infants.

124

125

126

127

128

129 **Table 1. Characteristics of pregnant women (n=636) by influenza vaccination status**130 **Characteristic** **Vaccinated** **Unvaccinated** **P-value**131 **n=406 (%)** **n=230 (%)**

132 \_\_\_\_\_

133 Mean age, years (range) 33.1 (21-45) 32.3 (18-45) 0.055

134 Mean gestational age, weeks (range) 19.3 (3-39) 21.6 (3-39) 0.003

135 Underlying disease 49 (12.2) 32 (14.0) 0.512

136 Influenza vaccination the past season 94 (23.2) 14 (6.1) <0.001

137 Mean no. of cohabitants (range) 1.7 (0-8) 1.8 (0-8) 0.147

138 Children <5 years 161 (39.8) 79 (34.5) 0.190

139 Mean no. of children <5 years (range) 0.5 (0-3) 0.4 (0-3) 0.325

140 No smoking during pregnancy 350 (93.1) 173 (84.0) 0.001

141 142 Smoking during pregnancy 26 (6.9) 33 (16.0)

143 \_\_\_\_\_

144

145

146

147

148

149

150

151 **Table 2. Morbidity (%) of pregnant women (n=636) by influenza vaccination status**

152	Type of morbidity	Vaccinated	Unvaccinated	P-value
153		n = 406 (%)	n = 230 (%)	
154	Influenza*	6 (1.5)	6 (2.6)	0.314
155	Febrile episode	17 (4.2)	13 (5.7)	0.402
156	ARI	115 (28.3)	50 (21.7)	0.069
157	ILI	11 (2.7)	11 (4.8)	0.169
158	Pneumonia	2 (0.5)	4 (1.7)	0.118

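### The odds ratio of 0.6 printed for no smoking contradicts Table 1; it almost certainly belongs to smoking, and the reference category is not stated

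*SAP*

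**What the plan says.** The Statistical analysis section specifies a logistic regression for factors associated with having been vaccinated in 2019-2020, with odds ratios and confidence intervals. The Results give its output just after describing the full analysis set ("Of the 855 pregnant women, 525 (61.4%) were vaccinated against influenza and 330" declining). The sentence opens with "analysis the following variables were significantly associated with a history of" vaccination and lists three terms:

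- gestational age: "influenza vaccination in 2019-2020: lower gestational age (OR: 0.998; CI: 0.998" to 0.999;
- past-season vaccination, followed by the label of the third term: "influenza vaccination the past season (OR: 8.8; CI: 4.7-16.2), and no smoking";
- the figure for that third term: "during pregnancy (OR: 0.6; CI: 0.4-0.9".

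No reference category is given for smoking, and no unit for gestational age.

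Table 1 covers a smaller set ("Of the 855 pregnant women included in the analysis, 636 women were still pregnant" in the season). Its smoking rows, vaccinated first, read "No smoking during pregnancy 350 (93.1) 173 (84.0) 0.001" and "Smoking during pregnancy 26 (6.9) 33 (16.0".

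**The concern.** An odds ratio of 0.6 with an interval wholly below 1, attached to no smoking, says that non-smokers were less likely to be vaccinated. Table 1 shows that they were more likely to be. The two statements cannot both be taken as printed.

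The figure is a reported estimate from an analysis that the SAP specifies. Vaccination was accepted or refused, not randomised, so these odds ratios are how the document describes differences between the two groups. Anyone who lifts the number into a summary or a meta-analysis of predictors of uptake would carry the wrong sign.

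**Working it through.** **1. Table 1 reproduces itself.** Women with smoking data: vaccinated 350 + 26 = 376, unvaccinated 173 + 33 = 206. Non-smokers: 350/376 = 93.1% and 173/206 = 84.0%, as printed. Missing: 406 − 376 = 30 and 230 − 206 = 24, together 54. The chi-square p-value is 0.0005 without and 0.0008 with continuity correction (Fisher exact 0.0008), consistent with the printed 0.001.

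**2. Direction in Table 1.** Vaccinated among non-smokers: 350/(350 + 173) = 66.9%. Vaccinated among smokers: 26/(26 + 33) = 44.1%.

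**3. Crude odds ratio.**
- No smoking: (350 × 33)/(26 × 173) = 11550/4498 = 2.57.
- Standard error of the log: √(1/350 + 1/26 + 1/173 + 1/33) = 0.278.
- 95% CI: exp(0.943 ± 1.96 × 0.278) = 1.49 to 4.43.
- Smoking (reciprocals): 0.39 (0.23-0.67).

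**4. The printed figure.** The regression itself cannot be refitted from the document. The printed estimate and interval agree with each other: √(0.4 × 0.9) = 0.6. So the label or coding is the likely fault, not the interval. Reciprocals: 1/0.6 = 1.67, 1/0.9 = 1.11, 1/0.4 = 2.50.

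| Reading of 0.6 (0.4-0.9) | Odds ratio for no smoking | Table 1 crude, no smoking | Same direction? |
|---|---|---|---|
| Belongs to no smoking | 0.6 (0.4-0.9) | 2.57 (1.49-4.43) | No; intervals do not overlap |
| Belongs to smoking | 1.67 (1.11-2.50) | 2.57 (1.49-4.43) | Yes |

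**5. Could missing smoking data reverse Table 1?** Suppose all 30 vaccinated women with missing data smoked and none of the 24 unvaccinated did: (350 × 33)/(56 × 197) = 11550/11032 = 1.05. The odds ratio is still not below 1.

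**6. Could the women outside Table 1 reverse it?** They number 525 − 406 = 119 vaccinated and 330 − 230 = 100 unvaccinated. Assume that all 219 have smoking data.
- None of the 100 unvaccinated smoked. For a crude no-smoking odds ratio of 0.6, the odds of not smoking among vaccinated women must be 0.6 × 273/33 = 4.96. Of 376 + 119 = 495 vaccinated women, 495/5.96 = 83.0 would then smoke, so 83.0 − 26 = 57.0 of the 119 (48%).
- 16% of the 100 smoked, as in Table 1. The odds must be 0.6 × 257/49 = 3.15, which gives 495/4.15 = 119.4 smokers, or 93.4 of the 119 (about 78%).
- Even for the upper limit of 0.9, with no smokers among the 100, 32.6 of the 119 (27%) would have to smoke.

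Table 1 shows 6.9% smokers among vaccinated women.

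**7. The other two terms.** Mean gestational age in Table 1 is 19.3 weeks in vaccinated and 21.6 weeks in unvaccinated women. An odds ratio below 1 therefore fits higher gestational age, not lower. Past-season vaccination (OR 8.8) is labelled in its own direction: the 91.8% and 55.1% in the Results give (0.918/0.082)/(0.551/0.449) = 9.1.

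**The case against.** The strongest reply is that the words are right and only the pairing is loose. Lower gestational age, past-season vaccination and no smoking are each the level that goes with vaccination in Table 1. One unstated convention fits all three: the words name that level, while the odds ratio belongs to the underlying variable (higher gestational age, past vaccination, smoking). This stands. It would be too much to say that no convention can be inferred. But the convention is nowhere stated, and a reader who takes each odds ratio to refer to the words beside it gets the wrong sign for two terms of three.

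A second reply is that the regression and Table 1 differ in population and perhaps in adjustment. This stands for size. A reader might infer that 0.6 is suspect because the crude smoking odds ratio is 0.39. The document does not support that: 0.6 lies inside the crude interval of 0.23-0.67. Past-season vaccination also shows that sizes do not carry over: its crude odds ratio in Table 1 is (94 × 216)/(312 × 14) = 4.65, against about 9.1 from the percentages that precede the regression and 8.8 printed. For direction the reply is weak, given steps 5 and 6 of the working. Adjustment could in principle reverse a sign, but nothing in the document suggests that it did.

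A third reply is that nothing downstream depends on this term. That stands too. The IVE formula is a crude ratio of incidences, and the influenza model as described uses vaccination and age group only.

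**Conclusion.** The result is wrong as written: the pairing of no smoking with 0.6 (0.4-0.9) contradicts the document's own table. The figure almost certainly belongs to smoking versus no smoking; for no smoking it would be about 1.7 (about 1.1-2.5). The odds ratio for gestational age has the same mismatch.

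This rests on the Table 1 counts being correct, which step 1 supports, and on the women outside Table 1 not smoking at several times the Table 1 rate. The two bounds were taken separately, and adjustment cannot be checked. So almost certainly is as far as the evidence goes, and the exact regression value cannot be confirmed.

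A reader might infer that a confounder has been reversed and that the bias in IVE would be read the wrong way. The document does not support this. It reports no association between smoking and influenza, so smoking is not shown to confound anything here. Smoking enters neither the IVE formula nor the described influenza model, so no effectiveness estimate, interval or p-value changes. What changes is one reported predictor of vaccine uptake and the labelling of another.

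**What to change.** Check how smoking and gestational age were coded in the fitted model. Then print one of the following:

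- smoking during pregnancy versus no smoking, OR 0.6 (0.4-0.9); or
- no smoking versus smoking, OR about 1.7 (about 1.1-2.5), with exact values from the model output, since inverting rounded figures is approximate.

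State the reference category. Label the gestational-age odds ratio as per week or per day of higher gestational age, whichever the model used. Add one clause giving the number of women in the regression and whether the odds ratios are adjusted, so that readers do not expect them to match Table 1.

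If the check shows that 0.6 really was estimated for no smoking, the reversal against Table 1 needs an explanation in the text.

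The cost is one look at the model output and a revised sentence. No new data are needed, and no refit unless the check finds a coding error in the model itself.

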159	Healthcare seeking	5 (1.2)	5 (2.2)	0.359
160	Hospitalization	0 (0.0)	1 (0.4)	0.184
161	Use of antibiotics	11 (2.7)	7 (3.0)	0.807
162	Use of antivirals	3 (0.7)	4 (1.7)	0.245

163

164 \* laboratory-confirmed influenza

165 ARI: acute respiratory infection; ILI: influenza-like illness

166

167

168

169

170 **Table 3. Morbidity (%) of infants (n=474) by maternal influenza vaccination status**

171	Type of morbidity	Vaccinated	Unvaccinated	P-value
172		n = 281 (%)	n = 193 (%)	
173	Influenza*	4 (1.4)	4 (2.1)	0.59
174	Febrile episode	7 (2.5)	8 (4.1)	0.312
175	ARI	17 (6.0)	27 (14.0)	0.012
176	ILI	6 (2.1)	6 (3.1)	0.507
177	AOM	1 (0.3)	2 (1.0)	0.358
178	Pneumonia	0 (0.0)	1 (0.5)	0.227
179	Healthcare seeking	6 (2.1)	10 (5.2)	0.144
180	Hospitalization	0 (0.0)	1 (0.5)	0.277
181	Use of antibiotics	4 (1.4)	5 (2.6)	0.360
182	Use of antivirals	0 (0.0)	3 (1.6)	0.036

183

184 \* laboratory-confirmed influenza

185 ARI: acute respiratory infection; ILI: influenza-like illness; AOM: acute otitis media

186

187

188

189

190

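### The 95% CIs for vaccine effectiveness (28.4% to 55.6% in mothers, 4% to 51% in infants) cannot come from 12 and 8 cases, and they contradict the SAP's own p-values

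*SAP*

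**What the plan says.** The Statistical analysis section defines IVE as one minus the ratio of influenza incidence in vaccinated to unvaccinated women, times 100. It describes a two-group beta-binomial model with non-informative priors and sets significance at 0.05. It names no method for the confidence interval of the IVE.

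For mothers (Results, Estimation of IVE in pregnant women):
- The event total is given as "Twelve of the 636 pregnant women tested positive for influenza (8 cases of influenza" A/H3N2, with the rest A/H1N1 and B. They split as 6/406 vaccinated and 6/230 unvaccinated.
- The incidence in the two groups is said to differ, "however the difference was not statistically significant". The Table 2 influenza row reads "6 (1.5) 6 (2.6) 0.314".
- A few lines later: "The IVE of QIV against influenza was 43.5% (95% CI: 28.4%-55.6%) for" pregnant women.

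For infants (Results, Estimation of IVE in infants):
- "Overall, 8 of the 474 infants tested positive for influenza (5 cases of influenza" A/H3N2, with the rest A/H1N1 and B. The Table 3 influenza row reads "4 (1.4) 4 (2.1) 0.59", with groups of 281 and 193.
- Significance is confined to ARI and antiviral use. The IVE "for infants was estimated at 31.4% (95% CI: 4%-51%) in 2019-2020" follows.

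Both subsections then conclude, from a regression logit of -4.2, that vaccination gave statistically significant protection.

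**The concern.** A 95% interval for IVE that excludes 0% says the same thing as a test of no difference with p below 0.05. Here the intervals exclude 0% for comparisons that the same document reports with p=0.314 and p=0.59. They are also far too narrow for 12 and 8 events, because the precision of a risk ratio for a rare outcome is set almost entirely by the number of cases.

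Maternal influenza is the primary outcome, and infant influenza is the first-listed secondary outcome. A reader who takes the intervals at face value would conclude that effectiveness is established in both groups and known to within about 14 percentage points in mothers (half of 55.6 - 28.4). The counts are in fact compatible with anything from a substantially raised risk to more than 80% protection.

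**Working it through.** **Inputs.** Mothers: 6/406 vs 6/230 (Results text and Table 2). Infants: 4/281 vs 4/193 (Table 3).

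**1. The point estimates and p-values reproduce.**
- Mothers: RR = (6/406)/(6/230) = 230/406 = 0.5665, so IVE = 43.3%. The printed 43.5% is 1 - 1.47/2.6, a rounding difference.
- Infants: RR = (4/281)/(4/193) = 193/281 = 0.687, so IVE = 31.3%. The printed 31.4% is 1 - 1.42/2.07, again rounding.
- Uncorrected chi-square gives p = 0.3139 and 0.5899, matching the tables. Fisher's exact test gives 0.367 and 0.721.

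**2. Intervals from the counts.** SE(log RR) = sqrt(1/a - 1/n1 + 1/c - 1/n0), with limits RR × exp(±1.96 SE).
- Mothers: SE = sqrt(1/6 - 1/406 + 1/6 - 1/230) = sqrt(0.3265) = 0.571. RR limits are 0.185 to 1.736, so IVE is -74% to 82%.
- Infants: SE = sqrt(1/4 - 1/281 + 1/4 - 1/193) = sqrt(0.4913) = 0.701. RR limits are 0.174 to 2.713, so IVE is -171% to 83%.

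**3. What the printed intervals imply.** Implied SE = [ln(1 - L) - ln(1 - U)]/3.92.
- Mothers: ln(0.716/0.444)/3.92 = 0.122. Ratio 0.571/0.122 = 4.7, and 22 times too little variance. Matching that precision would take about 12 × 22 = 264 cases instead of 12.
- Infants: ln(0.96/0.49)/3.92 = 0.172. Ratio 0.701/0.172 = 4.1, and about 16.7 times too little variance. That would take about 8 × 16.7 = 134 cases instead of 8.
- Implied p-values: z = ln(0.5665)/0.122 = -4.66, p about 0.000003, against 0.314 stated; z = ln(0.687)/0.172 = -2.19, p about 0.03, against 0.59 stated.
- On these data the printed ranges carry about 32% and 37% confidence, not 95%.
- On the log scale the printed intervals centre at 1 - sqrt(0.716 × 0.444) = 43.6% and 1 - sqrt(0.96 × 0.49) = 31.4%. They therefore sit around the crude IVE, and only their width is wrong.

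**4. Other methods, including the SAP's own model.**

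| Method | Mothers | Infants |
|---|---|---|
| Printed in the SAP | 28.4% to 55.6% | 4% to 51% |
| Log risk ratio | -74% to 82% | -171% to 83% |
| Poisson rate ratio, Wald | -76% to 82% | -175% to 83% |
| Exact conditional | -112% to 85% | -269% to 87% |
| Posterior, Beta(0.5,0.5) | -75% to 82% | -173% to 83% |
| Posterior, Beta(1,1) | -68% to 81% | -153% to 81% |

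Six vague hyperpriors on the beta parameters (uniform to 10, 100, 1000 and 10000; Gamma(1,1); Gamma(0.001,0.001)) gave lower limits of -67% to -81% for mothers and -153% to -190% for infants. The upper limits were 81% to 82% and 81% to 84%. Under Beta(0.5,0.5) the posterior probability that IVE exceeds 0 is 0.84 for mothers and 0.71 for infants, short of the 0.975 that a 95% interval excluding 0 would require.

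**5. The regression logit does not support the intervals.** The value -4.2 matches the vaccinated group's own log-odds: ln(6/400) = -4.20 in mothers and ln(4/277) = -4.24 in infants. The between-group log odds ratio is -0.58 (95% CI -1.72 to 0.56) in mothers and -0.38 (-1.78 to 1.02) in infants. Both include 0.

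**The case against.** The strongest defence is that the intervals come from the Bayesian hierarchical model with an age term, not from the crude two-by-two table. That does not work. The priors are stated to be non-informative, so they add no information. Age is reported not to predict influenza, and adjusting for a non-predictive binary covariate cannot be expected to cut the variance by a factor of 17 to 22. A text-extraction fault is also implausible, because the counts appear consistently in text and tables and both intervals centre on the printed estimates.

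Three narrower points have some force:
- The document does not present effectiveness uniformly as established. It calls the maternal difference non-significant and leaves infant influenza off its list of significant differences. Its explicit claim of significant protection is tied to the logit of -4.2, not to the IVE intervals. This is fair, but it makes the document self-contradictory and does not correct the intervals. It also means that the fix must reach those sentences.
- No single interval is uniquely right with 6 or 4 events per group. The log-ratio method is a large-sample approximation, and the exact limits are clearly wider. This stands, but the choice does not affect the conclusion, because every method in the table includes 0.
- How the printed intervals were produced cannot be determined from the document. That is true, but the correction does not depend on knowing it.

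**Conclusion.** The concern holds. Both printed 95% intervals are incompatible with the counts in the same document, with standard errors 4.7 and 4.1 times too small, and both contradict its own p-values. The point estimates and the influenza p-values are sound to rounding. The intervals and the statements of significant protection are wrong. Intervals consistent with the data run from about -74% to 82% in mothers and -171% to 83% in infants, or wider by the exact method. Effectiveness against influenza was not demonstrated in either group. This rests on the printed counts being correct, on the stated definition of IVE, and on the stated non-informative priors. It must be corrected, because it affects the primary result.

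**What to change.** - Replace both intervals and name the method. Either the log risk ratio interval (mothers 43.3%, -74% to 82%; infants 31.3%, -171% to 83%) or the posterior interval for one minus the ratio of the two rates from the SAP's own beta-binomial model would serve. With a Beta(0.5,0.5) prior the latter is -75% to 82% and -173% to 83%. Use the same method for both groups and state the prior if the posterior is reported.
- State that effectiveness against influenza was not demonstrated in mothers or infants, in line with p=0.314 and p=0.59.
- Withdraw or reword the two conclusions of significant protection. Replace the logit of -4.2 with the between-group log odds ratio and its interval.
- Delete the duplicate IVE sentences that give the estimate without an interval.

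The cost is recalculation and text correction; no new data are needed. The reported precision becomes much less favourable.

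### The reported logit reduction of -4.2 is the log-odds of influenza in the vaccinated group, not a vaccine effect, so neither claim of significant protection is supported

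*SAP*

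**What the plan says.** Under Statistical analysis, the SAP sets out a beta-binomial model with one influenza probability per group (vaccinated, unvaccinated). It states that the success rate p_j "was the probability of influenza onset in mothers and" that n_j is the group size. The same section gives a separate formula for vaccine effectiveness (IVE), one minus the ratio of the two incidence rates, and a significance level of 0.05.

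Under Estimation of IVE in pregnant women, the regression result is that vaccination reduced "their logit to develop influenza by -4.2 (95% CI -3,7 -4,7), which indicates that" "influenza vaccination added a statistically significant protection to pregnant women". Under Estimation of IVE in infants, vaccination "of pregnant women reduced the logit of their infants to develop influenza by -4.2" ("95% CI -3.6, -4.9), which indicates that influenza vaccination during pregnancy" "added a statistically significant protection to young infants").

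The same sections also report the opposite. Influenza incidence differed "between vaccinated women (6/406; 1.47%) and unvaccinated women (6/230; 2.6"%), "however the difference was not statistically significant. Similarly, higher rates of" other outcomes are then listed. Table 2 gives p = 0.314 for influenza in mothers. Table 3 gives 4/281 against 4/193 and p = 0.59 for infants, and the text limits significant infant differences to ARI and antiviral use. IVE is given as 43.5% in mothers and 31.4% in infants.

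**The concern.** With six cases in each maternal group and four in each infant group, no comparison of the groups can give a logit difference of -4.2 with a tight interval. It is also odd that two populations with different stated effectiveness share the same coefficient. The printed value looks like the level of risk in one group, read as if it were the change produced by vaccination.

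Influenza in pregnant women is the primary outcome, and influenza in infants is a secondary one. A reader who relies on the regression sentences would conclude that protection had been demonstrated in both. A reader who relies on the tables would conclude that it had not.

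**Working it through.** **Inputs.** Mothers (Results text, Table 2): 6/406 vaccinated, 6/230 unvaccinated. Infants (Results text, Table 3): 4/281 and 4/193.

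**1. Do the SAP's table p-values reproduce?** Pearson chi-square without correction, N(ad − bc)² divided by the product of the four margins:
- Mothers: 636 × (6×224 − 6×400)² / (406×230×12×624) = 1.014, p = 0.314, as printed.
- Infants: 474 × (4×189 − 4×277)² / (281×193×8×466) = 0.290, p = 0.590, as printed.

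The tables are consistent with the counts.

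**2. What does -4.2 reproduce as?** Group log-odds = ln[x/(n − x)], SE = √[1/x + 1/(n − x)].

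| Group | Log-odds | SE | 95% interval |
|---|---|---|---|
| Mothers, vaccinated | ln(6/400) = -4.20 | 0.411 | -5.01 to -3.39 |
| Mothers, unvaccinated | ln(6/224) = -3.62 | 0.414 | -4.43 to -2.81 |
| Infants, vaccinated mothers | ln(4/277) = -4.24 | 0.504 | -5.22 to -3.25 |
| Infants, unvaccinated mothers | ln(4/189) = -3.86 | 0.505 | -4.85 to -2.87 |

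The vaccinated rows match the printed point estimate in both populations. The unvaccinated rows do not, nor do the pooled values (-3.95 mothers, -4.07 infants). Zero on this scale is a risk of 50%, so all four intervals exclude it. By the same reasoning, not being vaccinated would also count as significant protection.

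**3. Do the printed intervals reproduce?** Not as 95% intervals. With multiplier 1.2816 (80% coverage):
- Mothers: -4.20 ± 1.2816 × 0.411 = -4.73 to -3.67 (printed -4.7 and -3.7).
- Infants: -4.24 ± 1.2816 × 0.504 = -4.88 to -3.59 (printed -4.9 and -3.6).

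All four limits agree to one decimal. This supports the identification in step 2 and suggests that the 95% label is wrong as well.

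**4. Could -4.2 be a vaccine effect?** exp(-4.2) = 0.015 as an odds ratio. Applied to the unvaccinated odds:
- Mothers: (6/224) × 0.015 = 0.00040, so about 0.16 cases expected in 406 women. Six were seen (probability of six or more about 2 × 10⁻⁸).
- Infants: (4/189) × 0.015 = 0.00032, so about 0.09 cases expected in 281 infants. Four were seen (probability of four or more about 2 × 10⁻⁶).

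The implied effectiveness is about 98.5%, against the stated 43.5% and 31.4%.

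**5. The actual contrast.** Log OR = difference of the two group log-odds, SE = √(sum of the four reciprocal cell counts).
- Mothers: -4.20 + 3.62 = -0.58. SE = √(1/6 + 1/400 + 1/6 + 1/224) = 0.583. 95% CI -1.72 to 0.56; OR 0.56 (0.18 to 1.76); p = 0.32.
- Infants: -4.24 + 3.86 = -0.38. SE = √(1/4 + 1/277 + 1/4 + 1/189) = 0.713. 95% CI -1.78 to 1.02; OR 0.68 (0.17 to 2.76); p = 0.59.

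A simple Bayesian version, with independent Beta(0.5, 0.5) priors on the two probabilities, gives -0.58 (-1.72 to 0.57) and -0.38 (-1.79 to 1.03). With Beta(1, 1) priors the intervals are -1.68 to 0.52 and -1.71 to 0.94. All include zero.

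**The case against.** - **The identification is an inference.** No coefficient table or code is shown, and the SAP also mentions random-intercept logistic models and an age-group variable, so -4.2 might be an intercept or another baseline term. This is fair, but the match of both point estimates and all four limits makes the vaccinated-group reading hard to escape. In any case, no baseline term is a comparison between groups.
- **The SAP does define a contrast.** The IVE formula compares the two groups. That stands. The gap is that the reported logit is not tied to that formula or to any other difference between groups.
- **The null result is not hidden.** The text says openly that the maternal difference was not significant, and both point estimates favour vaccination. So the right description is that significance is unsupported and the document contradicts itself, not that the vaccine was shown to fail.
- **The figures in step 5 are unadjusted large-sample estimates from few events.** This is true, and they serve as a check. The beta-prior results agree with them. The SAP reports that age was not a predictor, so adjustment for age would not be expected to change the picture.
- **Other numbers also imply significance.** The printed IVE intervals (28.4% to 55.6% and 4% to 51%) exclude zero too. They are a separate defect, and correcting the logit sentences alone would leave that implication standing.

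**Conclusion.** The concern holds; the statements are wrong as written. The value -4.2 equals the log-odds of influenza in the vaccinated group in both populations and cannot be a vaccine effect, which would be about -0.58 in mothers and -0.38 in infants. Both 95% intervals include no effect, and they extend to benefit and to harm. Neither claim of statistically significant protection is supported, and both contradict the SAP's own p-values and IVE point estimates. This rests on the printed counts being right, which the reproduced p-values support. That -4.2 comes from the vaccinated group, and that its interval has 80% coverage, are inferred from the numerical match; the verdict does not depend on the coverage.

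**What to change.** 1. In Statistical analysis, name the vaccinated-minus-unvaccinated contrast as the estimand, either logit(p_vaccinated) − logit(p_unvaccinated) or the IVE already defined, and state that significance is judged on it.
2. Report that contrast from the specified model with a true 95% interval. The counts lead one to expect values close to -0.58 (-1.72 to 0.56) for mothers and -0.38 (-1.78 to 1.02) for infants. If group log-odds are kept, label them as such, show both groups and correct the intervals.
3. Withdraw both statements of statistically significant protection, so that the text agrees with Tables 2 and 3.
4. Re-derive the IVE intervals at the same time. A large-sample interval for the rate ratio from the same counts runs from about -74% to 82% in mothers and from about -171% to 83% in infants.
5. As a minor wording point, define y_j as the number with influenza, since the present description of it as vaccine responders does not fit the definition of p_j.

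The cost is a change of wording and the re-reporting of one contrast and its interval per population. No new data are needed.
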